Exposure-adjusted on-treatment cumulative LFT elevations will also be summarized for treated subjects with the number and percentage of subjects with LFT elevations, along with patient-years and exposure-adjusted rates based on exposure up to time of first LFT elevation (see Section 4.8.2).

By-subject longitudinal LFT plots will display all normalized results (i.e., LFT ratio of value to ULN) regardless of study period for AST, ALT, ALP and TBL on the y-axis versus study week of laboratory result on the x-axis for treated subjects with any of the following LFT elevations during a safety analysis period (pre-treatment, on-treatment, follow-up): ALT $> 3 \times$ ULN; AST $> 3 \times$ ULN; TBL $> 2 \times$ ULN; ALP $> 2 \times$ ULN. Study week is defined as study day/7 (see Section 5.5). Each figure will also display treated migraine onsets, start of the on-treatment safety analysis period, and start of the follow-up safety analysis period.

Additionally, an evaluation of Drug-Induced Serious Hepatotoxicity (eDISH) scatter plot will display the maximum TBL ratio of value to ULN on the y-axis versus the maximum ALT ratio of value to ULN on the x-axis, where the maxima will be in the same safety analysis period but not necessarily concurrent. Both axes will be on the \log_{10} scale. Ratios $< 0.1 \times$ ULN will be set to 0.1. Sample sizes in the legend will represent subjects with paired ratios. A horizontal reference line will be placed at $2 \times$ ULN, and a vertical reference line will be placed at $3 \times$ ULN. The lower left quadrant will be labeled “Normal Range”, the upper left quadrant will be labeled “Hyperbilirubinemia”, the lower right quadrant will be labeled “Temple’s Corollary”, and the upper right quadrant will be labeled “Possible Hy’s Law Range.” The following eDISH scatter plots will be produced for treated subjects: (1) on-treatment by enrollment group; (2) on-treatment by average rimegepant exposure; (3) on-treatment by average rimegepant exposure for the EOD+PRN dosing group; (4) on-treatment by enrollment group for treated subjects who

took ≥ 14 tablets per 4 weeks for ≥ 12 weeks; (5) by safety analysis period (pre-treatment, on-treatment, follow-up) across enrollment groups pooled; (6) on-treatment by enrollment group for treated subjects who took ≥ 20 tablets per 4 weeks for ≥ 4 weeks; (7) on-treatment by enrollment group for treated subjects with near-daily dosing.

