 - ≥ 14 tablets per 4 weeks for 4, 8, 12, 16, 20, ≥ 24 , ≥ 12 , and ≥ 4 weeks (the “ ≥ 12 weeks” category will support the subgroup “treated subjects who took ≥ 14 tablets per 4 weeks for ≥ 12 weeks” specified in Section 4.2.6)
 - ≥ 20 tablets per 4 weeks for 4, 8, 12, 16, 20, ≥ 24 , ≥ 12 , and ≥ 4 weeks
 - ≥ 25 tablets per 4 weeks for 4, 8, 12, 16, 20, ≥ 24 , ≥ 12 , and ≥ 4 weeks
- Total rimegepant exposure (tablets) summed across all subjects, derived by summing cumulative exposure across all subjects
- Total rimegepant exposure (patient-years), derived by summing (study drug end dose date – study drug first dose date + 1)/365.25 across all subjects.

This summary will also display quintiles (e.g., P20, P40, P60, P80, where “PX” denotes Xth percentile) for asterisked (“*”) continuous parameters to support the derivation of rimegepant exposure subgroups (see below). See Section 5.3 for derived dates.

eDiary exposure over time will assess the number of 4-week (28-day) intervals in which a subject exceeded select tablet counts in the LTT analysis period (see Section 5.4), where the number of 4-week intervals are not necessarily consecutive. For example, suppose a subject takes 20 tablets through 4 weeks (interval 1; LTT study days 1 to 28), 10 tablets after 4 weeks to 8 weeks (interval 2; LTT study days 29 to 56), 25 tablets after 8 weeks to 12 weeks (interval 3; LTT study days 57 to 84), and 15 tablets after 12 weeks to 16 weeks (interval 4; LTT study days 85 to 112). Thus, this subject is considered to have taken ≥ 14 tablets per 4 weeks for 12 weeks (i.e., intervals 1, 3 and 4), ≥ 20 tablets per 4 weeks for 8 weeks (i.e., intervals 1 and 3), and ≥ 25 tablets per 4 weeks for 4 weeks (i.e., interval 3). See Section 5.5 for the definition of LTT study days.

eDiary exposure will also be summarized by subgroup level and overall for treated subjects for all subgroups of interest described in Section 4.2.6.

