- TEAEs occurring in $\geq 2\%$ of subjects in any enrollment group after rounding. Percentages will be displayed rounded to integers, and AEs will be displayed in alphabetical order by SOC and PT.
- AEs occurring in $\geq 2\%$ of subjects in any enrollment group or subgroup level[^]
- AEs occurring in $\geq 5\%$ of subjects in any enrollment group by severity (primary safety endpoint, see Section 4.6.1)
- AEs occurring in $\geq 10\%$ of subjects in any enrollment group
- Exposure-adjusted AEs
- AEs related to study drug by severity*
- AEs related to study drug occurring in $\geq 2\%$ of subjects in any enrollment group or subgroup level[^]
- SAEs (primary safety endpoint, see Section 4.6.1)*
- Exposure-adjusted SAEs
- AEs leading to study drug discontinuation (primary safety endpoint, see Section 4.6.1)*
- Hepatic-related AEs by severity (secondary safety endpoint, see Section 4.6.2)[#]
- Hepatic-related SAEs[#]
- Hepatic-related AEs leading to study drug discontinuation (secondary safety endpoint, see Section 4.6.2)[#]
- Additional AEs of special interest: potential drug abuse[^]; CV; suicidality. Potential drug abuse AEs will be displayed in alphabetical order by severity and PT without SOC.

Endpoints marked with “*” will also be summarized by subgroup level and overall for all subgroups of interest specified in Section 4.2.6. Endpoints marked with “#” will also be summarized by subgroup level and overall only for extrinsic exposure factors (see Section 4.2.6). Endpoints marked with “^” will also be summarized by subgroup level and overall only for key extrinsic exposure factors (see Section 4.2.6).

Refer to the BHV3000 Core SAP for exposure-adjusted AEs. Calculations for on-treatment exposure-adjusted AEs will set reference start date to the study drug first dose date, reference end date to the study drug end dose date, and reference last date to the study drug last dose date + 7 days.

Follow-up AEs

Follow-up AEs will be summarized by SOC and PT for follow-up subjects by enrollment group and overall for the following endpoints:

- AEs by severity
- SAEs.

AEs in All Safety Analysis Periods Combined

AEs in all safety analysis periods combined (i.e., pre-treatment, on-treatment, and follow-up) will be summarized by SOC and PT for treated subjects by enrollment group and overall for the following endpoints:

- AEs leading to study drug discontinuation (primary safety endpoint, see Section 4.6.1)

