5.3 Derived Dates

Derived dates for defining analysis periods are defined as follows:

- OP start date/time: Earliest complete date during the screening epoch in the eDiary.
- OP end date/time: Latest complete date during the screening epoch in the eDiary.
- LTT start date/time: Earliest complete date during the treatment epoch in the eDiary.
- LTT end date/time: Latest complete date during the treatment epoch in the eDiary.
- Study drug first dose date/time: Earliest complete date where subjects indicated that they took medication during the treatment epoch in the eDiary.
- Study drug end dose date/time: Latest complete date where subjects indicated that they took medication during the treatment epoch in the eDiary.
- Study drug last dose date/time: Study drug end dose date derived only for subjects who have non-missing completion status on the Study Exit Status CRF. Thus, in an interim analysis, all post-treatment data will be included for a subject who is still on study. At the last database lock, the last dose date will be equal to the end dose date for treated subjects.
- EOT visit date: Maximum of the following: (1) LTT end date/time; (2) latest complete visit date excluding folder name “follow-up safety visit” on the Visit Date CRF. This is derived only for subjects who have non-missing completion status on the Study Exit Status CRF.

- Last contact date: (1) Complete death date, if it exists; (2) otherwise, the maximum complete date of the following: AE start/stop; ECG; eDiary; enrollment; informed consent; laboratory collection; non-study medication start/stop; physical measurement; procedure; rating scale; questionnaire; screening; study completion/discontinuation; vital sign; visit.

No imputations are performed on these derived dates. Complete dates are those with valid, non-missing day, month, and year.

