5.4 Analysis Periods

Analysis periods are defined as follows:

- Observational Period (OP): measurement date/time on or after the OP start date/time through the OP end date/time. This period is used to assess the number of migraine days per 4 weeks during the OP.
- Pre-treatment: measurement date/time on or before the study drug first dose date/time. This period is used to derive baseline values, and to assess safety and outcomes research endpoints.
- Post-enrollment: measurement date/time after the IWRS enrollment date/time through the EOT visit date + 7 days. This period is used to derive analysis visit windows for slotting observations.
- Follow-up: measurement date after the EOT visit date + 7 days. This period is used to slot observations.
- Long-term treatment (LTT): measurement date/time on or after the LTT start date/time through the LTT end date/time. This period is used to assess the number of migraine days per 4 weeks and number of tablets taken during LTT.
- On-treatment safety: measurement date/time after the study drug first dose date/time through the study drug last dose date + 7 days. Note that AEs with imputed start date equal to the study drug first dose date are part of this period (refer to the BHV3000 Core SAP for AE start date imputation). This period is used to assess safety endpoints on treatment.
- Follow-up safety: measurement date after the study drug last dose date + 7 days. This period is used to assess safety endpoints during follow-up.

See Section 5.3 for derived dates for determining analysis periods. If measurement time is missing or not collected, then the measurement date will be compared to the derived date.

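### As most naturally read, exposure-adjusted AE rates count events to last dose + 7 days but stop patient-time at the last tablet, which would overstate rates by about 8% in the 12-week EOD+PRN group and 2% in the 52-week groups

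*SAP*

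**What the plan says.** - **Event window.** SAP 5.4 defines the on-treatment safety period as "measurement date/time after the study drug first dose date/time through the study drug last dose date + 7 days". On-treatment AEs are counted in that window.
- **Dates for the rates.** SAP 4.8.2 starts the calculation at the first dose and then gives two closing dates: "reference end date to the study drug end dose date, and reference last date to the study drug last dose date + 7 days". Only the second carries the extra 7 days.
- **Formula.** It is not in this SAP: "Refer to the BHV3000 Core SAP for exposure-adjusted AEs".
- **What the dates are.** SAP 5.3 defines the end dose date by the diary: "Study drug end dose date/time: Latest complete date where subjects indicated that they took medication during the treatment epoch in the eDiary". The last dose date is the same date, but it is derived only for subjects with a completion status on the exit form. "At the last database lock, the last dose date will be equal to the end dose date for treated subjects".
- **Patient-years elsewhere.** The exposure summary in SAP 4.8.1 has a total "derived by summing (study drug end dose date – study drug first dose date + 1)/365.25 across all subjects", with no 7-day extension.
- **LFT rates.** SAP 4.6.3.1 plans "patient-years and exposure-adjusted rates based on exposure up to time of first LFT elevation" and cross-refers to 4.8.2.
- **Treatment length.** Protocol 7.2.2 gives up to 12 weeks for the EOD+PRN group and up to 52 weeks for the two PRN groups.

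**The concern.** A rate needs events and time at risk drawn from the same window. If a subject can still have a countable event in the 7 days after the last tablet but adds no time for those days, the denominator is too small. The missing time is a fixed 7 days per event-free subject, so it weighs most where treatment is short.

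That matters here because the enrollment groups are treated for 12 or 52 weeks. In the SAP 4.8.2 list of on-treatment tables, the exposure-adjusted AE and SAE tables are the only ones that allow for length of treatment. A bias that itself depends on treatment length would raise the EOD+PRN group, which has the densest scheduled dosing, relative to the others.

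The 7-day tail need not be empty. For LFTs, the end-of-treatment or early-termination draw can fall after the last tablet and within 7 days of it. By Protocol Tables 1 and 2, that draw is one of 4 scheduled post-baseline treatment-period draws in the EOD+PRN group (Weeks 2, 4, 8, 12), against one of 14 in the 52-week groups.

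**Working it through.** The documents state no exposure-adjusted rate or expected patient-years, so there is no figure of the plan's own to reproduce.

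**Step 1: which date ends patient-time?** Two closing dates imply two roles. The one with + 7 days matches the event window in SAP 5.4. The other matches the patient-years in SAP 4.8.1. At an interim lock the last dose date is not derived for ongoing subjects, so the end dose date is the only one of the two that exists for every treated subject. This points to the end dose date as the end of time, but no sentence says so.

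**Step 2: size of the gap.** At final lock, last dose equals end dose, so the two dates differ by exactly 7 days.

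**Step 3: overstatement for rare events.** Let T be days from first to last tablet, with the on-treatment hazard continuing unchanged through the tail. The relative overstatement is (T + 7)/T − 1 = 7/T.
- EOD+PRN, T = 84: 7/84 = 8.3%.
- 52-week PRN, T = 364: 7/364 = 1.9%.
- Between-group distortion: 1.0833/1.0192 = 1.063, about 6%.
- PRN (2-8) with about 1200 subjects at 52 weeks and about 20 at 12 weeks: mean T = (1200 × 364 + 20 × 84)/1220 = 359.4 days; 7/359.4 = 1.95%.
- All groups at planned size: missing time 2000 × 7/365.25 = 38.3 patient-years, against (1800 × 364 + 200 × 84)/365.25 = 1840 patient-years, about 2%.

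**Step 4: sensitivity.** Dropout, tail hazard and event rates are not given, so these are assumed ranges. For first events with constant hazard L, the overstatement is [1 − exp(−L(T + 7))]/[1 − exp(−L·T)] − 1. Dropout is exponential with the same hazard in both groups, and mean T is used in 7/T.

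| Assumption | EOD+PRN | 52-week PRN | Between-group distortion |
|---|---|---|---|
| Rare events, full treatment | 8.33% | 1.92% | 1.063 |
| First event, 0.5 per patient-year | 7.83% | 1.48% | 1.063 |
| First event, 1 per patient-year | 7.34% | 1.11% | 1.062 |
| 20% dropout by Week 52 | 8.55% | 2.15% | 1.063 |
| 50% dropout by Week 52 | 9.02% | 2.67% | 1.062 |
| Tail hazard half of on-treatment | 4.17% | 0.96% | 1.032 |
| Tail hazard zero | 0% | 0% | 1.000 |

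The distortion stays near 6% under dropout and for common events. What moves it is the hazard in the tail.

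**Step 5: after alignment.** If events and time end on the same date, the overstatement is 0% in every group under constant hazard.

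**Step 6: interim lock.** For an ongoing subject the last dose date is missing. SAP 5.3 says that all post-treatment data are then included, so the event window is open-ended while the end dose date remains the last reported tablet. The gap is then not fixed at 7 days.

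**The case against.** The strongest objection is that the deciding rule is in a document we do not have. SAP 4.8.2 only assigns values to three dates. If the Core SAP ends event-free time at the reference last date, there is no mismatch for completed subjects. That stands, and it is why the conclusion is conditional.

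Other objections, and what remains of them:
- **The 4.8.1 patient-years are not the rate denominator.** They belong to the exposure summary and do not stop at an event. This is correct; they show how the SAP measures time, not how the rate is computed.
- **The LFT link is a cross-reference only.** The dates in 4.8.2 are given for AEs. This stands, so the LFT table is probably, not certainly, affected.
- **The tail hazard is assumed.** This stands; the range is shown above.
- **The consequence is limited.** The estimands in SAP 2.3.1 and 2.3.2 are numbers and percentages of subjects, the trial is not randomized, and the CSR follows final lock (SAP 4.3). All true. It limits the importance of the point but does not remove it.

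A reader might infer that rates in the 12-week group are inflated fourfold. They are not: 8.3/1.9 is a ratio of two small overstatements. It also varies with the assumptions (3.4 with 50% dropout, 6.6 at one first event per patient-year), so it is a poor summary. Nor is there a separate second 12-week group in the tables: SAP 4.2.1 places the roughly 20 12-week PRN subjects within PRN (2-8).

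**Conclusion.** The point holds in conditional form. On the most natural reading of SAP 4.8.2, events run to last dose + 7 days and event-free time ends at the last tablet. If so, and if the on-treatment hazard persists through the tail, exposure-adjusted AE and SAE rates are overstated by about 8% in the EOD+PRN group and about 2% in the 52-week PRN groups at full treatment, with a between-group distortion of about 6%. At half that tail hazard the figures are about 4%, 1% and 3%; at zero hazard there is no effect.

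The documents do not support saying that the rates are inflated as a matter of fact, because the formula is not shown. Nor do they support extending the problem to the primary or secondary endpoints, which are crude counts and percentages. The interim-lock gap is a separate consequence of the same dates and disappears at final lock. The point is worth correcting, but it does not threaten the trial's main results.

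**What to change.** In SAP 4.8.2, state which date ends patient-time for subjects without the event. Set it to the earlier of last dose + 7 days and last contact, or to the data cut-off for subjects still ongoing at an interim lock. Give both closing dates this same value, so that events and time agree whichever one the Core SAP formula uses. Apply the rule to AEs, SAEs and the LFT elevations in 4.6.3.1, so that it matches the on-treatment window in 5.4. Keep the first-to-last-tablet patient-years in 4.8.1 as an exposure summary only.

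Check the wording against the Core SAP. If the Core SAP already aligns the two windows, including for ongoing subjects, one confirming sentence in 4.8.2 closes the point.

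The cost is a short edit and that check; no new data are needed. Reported rates become slightly lower, and rate denominators will no longer equal the exposure total in 4.8.1, which a table footnote should say.

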# 4.3.4 Follow up Safety Visit

Patients will return to the study site 14 days after the Week 12/52/EOT Visit (+/- 2 days) to collect laboratory tests, vital signs, electrocardiography, and AEs. Investigators should assess patients for AEs consistent with drug dependency or withdrawal effects and report as appropriate (see Section 7.4).

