4.6 Safety, Tolerability and Other Evaluations

Unless otherwise noted, all primary, secondary and exploratory analyses will be conducted using all treated subjects. All data will also be included in by-subject listings that will include enrollment group and time point (as applicable). The terms “on-treatment” and “follow-up” will apply to the on-treatment and follow-up safety analysis periods, respectively (see Section 5.4) unless specified otherwise.

Outcomes research (non-safety) questionnaires and rating scales are MSQoL, MIDAS, CGI-C, PoM, and SM (see Section 2.3.3). MSQoL, MIDAS, and CGI-C will be summarized as continuous parameters at baseline and each scheduled visit over time. Post-baseline measurements will be slotted into analysis visit windows in the post-enrollment and follow-up analysis periods (see Section 5.4). If a subject has multiple values in an analysis visit window, then the non-missing value closest to the target date for the visit will be used; in the case of a tie, the latest value collected will be used. See Sections 4.5, 5.4 and 5.5 for definitions of baseline, analysis periods, and analysis visit windows, respectively.

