4.8.2 Adverse Events

Refer to the BHV3000 Core SAP for AE start date imputation, AE counting rules, definition of treatment-emergent adverse events (TEAEs), and definition of AEs related to study drug.

Tables will present the number and percentage of subjects experiencing AEs by SOC and PT, unless specified otherwise.

A by-subject listing of all AEs will be provided for screened subjects that will flag on-treatment and treatment-emergent AEs. Additional by-subject listings of deaths, SAEs, AEs leading to study drug discontinuation, hepatic-related AEs, and AEs of special interest (i.e., potential drug abuse, CV, and suicidality) will be provided for screened subjects. Refer to the BHV3000 Core SAP for listing content and AEs of special interest.

AE Overview

An AE overview without SOC and PT will present the number and percentage of subjects with any the following AEs: any AE; severe AE; AE related to study drug (unlikely related, possibly related, or related); SAE; SAE related to study drug; AE leading to study drug discontinuation; AE leading to death; hepatic-related AE; severe hepatic-related AE; hepatic-related SAE; hepatic-related AE leading to study drug discontinuation; potential drug abuse AE; CV AE; suicidality AE. An AE overview will be produced for each the following analysis periods and populations:

- Pre-treatment AEs for screened subjects by enrollment group and overall
- Pre-treatment AEs for treated subjects by enrollment group and overall
- TEAEs for treated subjects by enrollment group and overall
- On-treatment AEs for treated subjects by enrollment group and overall
- On-treatment AEs for treated subjects by subgroup level and overall for all subgroups of interest specified in Section 4.2.6
- Follow-up AEs for follow-up subjects by enrollment group and overall.

Pre-Treatment AEs

Pre-treatment AEs will be summarized by SOC and PT by enrollment group and overall for screened subjects for the following endpoints:

- AEs
- SAEs.

Pre-treatment AEs will be summarized by SOC and PT for treated subjects by enrollment group and overall for the following endpoints:

- AEs by severity (total, mild, moderate, severe, moderate or severe, not reported)
- SAEs.

On-Treatment AEs

On-treatment AEs will be summarized by SOC and PT for treated subjects by enrollment group and overall for the following endpoints:

- AEs by severity*
- TEAEs by severity

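### Follow-up AE percentages cover windows of unequal length, longest in PRN 2-8, so a moderate EOD+PRN excess arising more than 7 days after the last tablet could be hidden

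*SAP*

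**What the plan says.** SAP 4.8.2 sets the default for AE tables: "Tables will present the number and percentage of subjects experiencing AEs by SOC and PT, unless specified otherwise". For the period after treatment, "Follow-up AEs will be summarized by SOC and PT for follow-up subjects by enrollment group and overall for the following endpoints": AEs by severity, and SAEs. An AE overview is also planned for this period. Exposure-adjusted AEs and SAEs are listed only under the on-treatment heading, and reference dates are given only there: "Calculations for on-treatment exposure-adjusted AEs will set reference start date to the study drug first dose date".

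SAP 4.6 fixes which period is meant. The terms on-treatment and follow-up "will apply to the on-treatment and follow-up safety analysis periods, respectively". SAP 5.4 then defines "Follow-up safety: measurement date after the study drug last dose date + 7 days", with no upper limit. The anchor comes from SAP 5.3: "Study drug end dose date/time: Latest complete date where subjects indicated that they took medication during the treatment epoch in the eDiary". At final lock the last dose date equals that date. Under SAP 3, a follow-up subject is a treated subject whose last contact falls in this period.

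Protocol 4.3.4 puts the closing visit 14 ± 2 days after EOT in every group and gives it a purpose: "Investigators should assess patients for AEs consistent with drug dependency or withdrawal effects". Under Protocol 4.1, EOD+PRN subjects take a scheduled tablet every second day whether or not they have a migraine. PRN subjects take a tablet only when a migraine starts.

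**The concern.** One end of the window is tied to the last tablet and the other, in practice, to EOT. An EOD+PRN subject who follows the schedule takes the last tablet a day or two before EOT. A PRN subject may have taken it days or weeks before. That subject's follow-up window is longer and can open while the treatment phase is still running.

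At equal daily AE rates, the group with the longer window shows the higher percentage. EOD+PRN is the group dosed on a regular schedule, and the closing visit is where sites are asked to look for dependency or withdrawal effects. A modest real excess in that group could appear as no difference, or as a slightly lower percentage, beside PRN 2-8. No planned table reports follow-up time or equalises the windows.

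The SAP anticipates the overlap for continuous safety parameters: SAP 4.8 gives values from Weeks 2 to 56 that fall in the follow-up safety period their own Follow-up EOT row. It has no counterpart for AEs.

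**Working it through.** **The plan's own figures.** The only sample-size figures are the zero-event bounds in SAP 4.1. They reproduce: 1 − 0.05^(1/2000) = 0.001497 and 1 − 0.05^(1/800) = 0.003738, against 0.0015 and 0.00375. They say nothing about follow-up, and this point does not rest on them.

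**Inputs from the documents.** The window opens after last tablet + 7 days (SAP 5.4). The closing visit is EOT + 14 ± 2 days (Protocol 4.3.4). Planned group sizes are about 1200, 600 and 200 (Protocol 5).

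**Assumptions, not in the documents.**
- PRN tablets fall at random, at t tablets per 4 weeks, so the mean gap to EOT is 28/t days.
- PRN tablet rates span the group labels uniformly (2 to 8, and 9 to 14 per 4 weeks).
- EOD+PRN subjects dose up to EOT, with a gap of 1 or 2 days (mean 1.5).
- The last contact is the closing visit.
- The daily AE rate h is constant.

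**Window length** = gap + 14 − 7 = gap + 7 days.

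| Group or rate | Mean gap (days) | Mean window (days) | Ratio to 8.5 |
|---|---|---|---|
| EOD+PRN | 1.5 | 8.5 | 1.00 |
| PRN, t = 2 | 14.0 | 21.0 | 2.47 |
| PRN, t = 4 | 7.0 | 14.0 | 1.65 |
| PRN, t = 5 | 5.6 | 12.6 | 1.48 |
| PRN, t = 8 | 3.5 | 10.5 | 1.24 |
| PRN, t = 14 | 2.0 | 9.0 | 1.06 |
| PRN 2-8, uniform mix | 28 × ln(8/2)/6 = 6.5 | 13.5 | 1.59 |
| PRN 9-14, uniform mix | 28 × ln(14/9)/5 = 2.5 | 9.5 | 1.12 |

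Two sensitivities on the EOD+PRN side, against PRN 2-8:
- If 80% of scheduled doses are taken, the window is 9.0 days and the ratio is 13.5/9.0 = 1.50.
- If the last tablet always falls the day before EOT, the window is 8.0 days and the ratio is 13.5/8.0 = 1.69, the outer edge.

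A window opens before EOT when the gap exceeds 7 days. Under these assumptions that happens in 28% of PRN 2-8 subjects and 3% of PRN 9-14 subjects.

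**Effect on the crude percentage.** This is the average of 1 − exp(−h × window) over simulated windows (400,000 draws).

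| h per day | PRN 2-8 | PRN 9-14 | EOD+PRN, rate ratio 1.0 | 1.5 | 2.0 |
|---|---|---|---|---|---|
| 0.002 | 2.7% | 1.9% | 1.7% | 2.5% | 3.3% |
| 0.005 | 6.5% | 4.6% | 4.2% | 6.2% | 8.1% |
| 0.01 | 12.4% | 9.0% | 8.1% | 11.9% | 15.6% |

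At h = 0.005, a true EOD+PRN rate ratio of 1.5 appears against PRN 2-8 as 6.2% against 6.5%, a ratio of 0.96. With 200 and 1200 subjects, the EOD+PRN percentage is at or below the PRN 2-8 percentage about 58% of the time. On person-time the same case is 0.75 against 0.50 events per 100 patient-days, which recovers 1.5. At a true ratio of 2 the excess shows on average, although chance alone still puts EOD+PRN at or below PRN 2-8 in 33%, 22% and 12% of cases at the three rates.

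**The case against.** The other side is substantial.

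- **No planned inference is affected.** The primary and secondary estimands in SAP 2.3 are on treatment. Groups are not randomised and differ in migraine history and treatment duration, so person-time would not make the contrast causal. This stands, and it limits the point to presentation.
- **The first post-dose week is elsewhere.** Events within 7 days of the last tablet are on-treatment under SAP 5.4 and enter the exposure-adjusted tables. A reader might infer that all withdrawal events are at risk of being masked. The documents do not support that, because only later events reach the follow-up table.
- **A constant rate may not suit a withdrawal effect.** If the effect fades with time since the last dose, late PRN days add few such events and the crude percentages are distorted less. Dividing by long PRN follow-up could then dilute the PRN rate. This also stands, and is why a fixed window should accompany person-time.
- **The size is assumed.** EOD dosing may stop before a late EOT visit, and PRN subjects may treat mild attacks too. Either would narrow the gap. Early discontinuers are not modelled. In the other direction, SAP 4.2.6 provides for average use below 2 tablets per 4 weeks, and at 1 tablet the mean window would be 28 + 7 = 35 days.
- **Some of this can already be seen.** AE listings and summaries of time on drug and time to last contact allow a rough reconstruction, but no planned table does it.

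The BHV3000 Core SAP was not available. SAP 4.8.2 relies on it for the exposure-adjusted method but sets reference dates only for the on-treatment period.

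**Conclusion.** The mechanism follows from the text: crude percentages, a window opening at last tablet + 7 days, a closing visit fixed to EOT, and no adjustment for follow-up time. That PRN windows are longer is inferred from the dosing rules. Its size rests on the assumptions listed above.

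On those assumptions, the table could hide an EOD+PRN excess of about 1.5- to 1.6-fold against PRN 2-8. Against PRN 9-14 the figure is only about 1.1-fold. It would be wrong to extend the larger figure to all as-needed subjects, or to conclude that a large excess would be cancelled: a twofold one remains visible on average.

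SAEs have a separate problem. Protocol 8.1.2 requires all SAEs only up to EOT, and later ones only if believed related to study drug or procedures. Nearly all of an adherent EOD+PRN window lies after EOT, while part of many PRN 2-8 windows lies before it. Ascertainment therefore differs as well as duration, and person-time does not correct that.

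This is a low-severity point, worth acting on because the remedy is cheap.

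**What to change.** In SAP 4.8.2, keep the crude follow-up tables and add:

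1. Follow-up AEs by enrollment group restricted to those starting 8 to 12 days after the last dose, among subjects whose last study visit is at least 12 days after the last dose. Day 12 is the limit because a tablet taken on the EOT date and a closing visit at EOT + 12 give exactly 12 days. A cut-off at day 14 or 15 would not be covered by every completer who attends, and adherent EOD+PRN subjects would be the likeliest to fall short.
2. Follow-up AEs per patient-time by enrollment group, from last dose + 8 days to the last study visit date (the follow-up safety visit if attended), with follow-up person-time shown for each group. The last contact date should not be the end point: SAP 5.3 builds it partly from AE and medication dates, so having an AE could lengthen a subject's person-time.
3. A footnote to the follow-up SAE table stating the collection limit in Protocol 8.1.2. The schedules in Protocol Tables 1 and 2 still mark AE and SAE assessment at the follow-up visit, so these passages should be reconciled.

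The cost is SAP wording and one or two tables. No new data are needed; the last study visit date must be derived from visit dates already collected. The fixed window omits later events, which remain in the crude table.
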